Patient data: The Institute programmer will work with clinical study staff to operationally define all study data elements and will use a programmatic data pull to obtain all data elements from Clarity that can be obtained using this method. A Redcap database will be constructed by the study programmer containing the expected 640 patients, and will be used by chart auditors to manually chart audit data elements that cannot be obtained programmatically.

Staff data: The study team will receive a data file of staff survey responses collected as part of the QI project. Surveys will be administered using REDCap or on paper at the time of the simulation. Simulation center staff will send survey data to the Institute study team via secure file transfer.

d) Outcomes/endpoint and other variable definitions, and instruments used:

A data source of “EMR” means that the data elements can be gathered by an Institute programmer using a programmatic data pull of Clarity (EMR) data. “Chart” means that the data

element will be manually abstracted from the EMR. The detailed listing of variables below will serve as the start of a data dictionary. The study programmer will add detailed codes to this document as the project progresses to document codes used to define each data element. The chart audit tool will be built in Redcap and does not yet exist. However, the listing of variables below with a data source of "chart" indicates which variables will be collected through the chart audit.

Variable name	Data Source	Purpose	Measurement scale
Patient data			
Hospital at which second stage cesarean section occurred (Regions, Methodist)	EMR	Key grouping variable	Binary
Time period of cesarean section (pre or post Regions simulation)	EMR	Key grouping variable	Binary
Fetal station at time of delivery	Chart	Covariate	Continuous
Push vs pull method	Chart	Description	Binary
Use of instrumentation (vacuum or forceps)	EMR	Covariate	Binary
Person doing the head extraction (staff or resident)	EMR	Covariate	Binary
Maternal BMI	EMR	Description	Continuous
Fetal weight	EMR	Description	Continuous
Cesarean indication (maternal or fetal)	EMR	Description	Binary
Gestational age at the time of c/s	EMR	Description	Continuous
Parity	Chart	Description	Continuous
Length of second stage	EMR	Covariate	Continuous
Use of tocolytics at the time of c/s	Chart	Relationship to morbidity outcomes	Binary
Operative time	Chart	Secondary Study endpoint	Continuous

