Length of stay	EMR	Secondary Study endpoint	Continuous
Time from skin incision to delivery or uterine incision to delivery	Chart	Secondary Study endpoint	Continuous
Head pushed up from below prior to c/s	Chart	Relationship to morbidity outcomes	Binary
Previous c/s	Chart	Description	Binary
Extension of uterine incision	Chart	Component of Primary maternal study endpoint	Binary
Operative blood loss (codes as < 1000 mL vs. > 1000 mL for primary endpoint)	Chart	Component of Primary maternal study endpoint	Continuous, binary
Number of blood transfusions (coded as 0 vs. any for primary endpoint)	Chart	Component of Primary maternal study endpoint	Continuous, binary
Endometritis within 6 weeks postpartum	EMR	Component of Primary maternal study endpoint	Binary
Wound infection within 6 weeks postpartum	EMR	Component of Primary maternal study endpoint	Binary
UTI during maternal admission	EMR	Secondary study endpoint	Binary
Bladder/ureteral/urethral injury	Chart	Secondary study endpoint	Binary
Type of uterine incision made	Chart	Description	Continuous
Maternal discharge Hemoglobin	EMR	Secondary study endpoint	Continuous
APGAR score at 5 minutes (coded as <7 vs. >=7 for primary endpoint)	EMR	Component of Primary infant study endpoint	Continuous, binary
APGAR score at 1 minute	EMR	Secondary study endpoint	Continuous

NICU admission	EMR	Component of Primary infant study endpoint	Binary
Umbilical artery pH <7.1	Chart	Component of Primary infant study endpoint	Binary
Fetal injury (fractures, head injury, brachial plexus injury)	EMR	Component of Primary infant study endpoint	Binary
Fetal death	EMR	Secondary study endpoint	Binary
Fetal hyperbilirubinemia	EMR	Secondary study endpoint	Binary
Uterine incision to delivery time (also categorized as <1 minute >=1 minute)	Chart	Secondary study endpoint	Continuous
Maternal discharge hemoglobin	Chart	Secondary study endpoint	Continuous
Medical staff confidence in handling second stage cesarean sections	QI Project Staff Survey	Secondary study endpoint	Continuous
Medical staff perceptions of second stage cesarean sections	QI Project Staff Survey	Secondary study endpoint	Continuous
Medical staff knowledge of interventions & medications for second stage cesarean sections	QI Project Staff Survey	Secondary study endpoint	Continuous
Medical staff teamwork when handling second stage cesarean sections	QI Project Staff Survey	Secondary study endpoint	Continuous

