Staff survey: The pre and post staff surveys are used for the QI project to assess staff perceptions of the required simulation training, and are included as the end of the narrative as appendices. These surveys use items developed for this project rather than existing tools. Surveys include a label to identify whether they are gathered before or after the simulation, and contain items such as confidence in handling second stage cesarean sections.

f) Statistical analysis plan

Descriptives (mean, standard deviation, proportion) and frequency distributions of all variables will be computed and examined for distribution shape, outliers, missing data, and implausible data. Tables of descriptive statistics summarizing patients in both care systems (Regions, Methodist)

will be created. Because there are only 2 primary outcomes (both of which are composite variables), there will be no control for multiple testing. Inferential analysis of secondary endpoints will be considered exploratory with the known limitation that multiple testing could yield type 1 errors. Covariates in regression analysis will be specified a-priori on the basis of theory and when such covariates are unbalanced in comparison groups.

Research question 1.1: Does the simulation protocol decrease a composite variable of maternal morbidity defined as a) extension of uterine incision, b) operative blood loss > 1000 mL, c) requirement of transfusion, d) wound infection within 6 weeks, and d) endometritis within 6 weeks, at Regions Hospital compared to morbidity over the same time period at Methodist Hospital?

Analytic sample: 480 maternal patients (120 Regions before/120 after simulation; 120 Methodist before/120 after simulation). Each sample of 120 is viewed as an independent sample.

Analytic approach: Logistic regression will be used to predict the composite maternal morbidity endpoint (0/1) from hospital (Regions, Methodist), time (pre or post simulation), and their interaction. Covariates will be included if needed as described earlier. Model-based proportions, standard errors, and 95% CIs for each hospital for each time point, change over time, and differential change over time by hospital will be computed. A significant hospital * time interaction and pattern of effects showing more improvement over time in Regions than Methodist will support the underlying hypothesis of differential improvement over time favoring Regions and potentially due to the effects of the simulation.

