Research question 1.2: Does the simulation protocol decrease a composite variable of infant morbidity defined as a) 5 minute APGARs <7, b) NICU admission, c) umbilical cord arterial pH <7.1, and d) fetal injury, at Regions Hospital compared to morbidity over the same time period at Methodist Hospital?

Analytic sample: 480 infant patients (120 Regions before/120 after simulation; 120 Methodist before/120 after simulation). Each sample of 120 is viewed as an independent sample.

Analytic approach: Same as 1.1, but uses the endpoint of composite infant morbidity

Research question 2.1: Does Regions hospital provider and team confidence regarding delivery of impacted fetal head increase after participating in simulation education?

Analytic sample: The 120 staff completing the pre and post simulation surveys, and sample of 80 completing the pre and 6 month surveys. This data is obtained from surveys from the QI project utilizing the required simulation training events.

Analytic approach: Descriptive statistics (mean, proportion) and 95% CIs will be used to summarize staff survey items at each time point, and change from pre-simulation to immediately post-simulation, and pre-simulation to 6 month post-simulation. Plots over time of key survey items will illustrate staff reactions and perceptions over time. Simple paired-data analyses (e.g., paired t-tests, McNemar's test) may be used to test change over time in key items or composites specified a-priori. Where possible, composites of multiple items will be summarized rather than individual items to reduce the number of comparisons and tests made.

Research question 2.2: Does implementation of the simulation protocol decrease morbidity of other individual secondary outcomes (see variables table) during the second stage of labor at Regions Hospital compared to morbidity over the same time period at Methodist Hospital?

Analytic sample: 480 infant/maternal patients (120 Regions before/120 after simulation; 120 Methodist before/120 after simulation). Each sample of 120 is viewed as an independent sample.

Analytic approach: Same as 1.1, but dependent variables for these analyses will include the individual component items of the primary endpoints, and variables listed as “secondary endpoints” in the variable table. Due to the large number of tests conducted, these analyses will be viewed as more exploratory.

Research question 2.4: Is duration of second stage related to maternal and perinatal complications?

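### Maternal discharge hemoglobin, an exploratory secondary endpoint, is analysed without an admission value and without a rule for transfused women

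*Combined protocol and SAP*

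**What the plan says.** The variable table in section 4 d) gives "Maternal discharge Hemoglobin" as a continuous secondary endpoint drawn from the EMR. The same variable reappears near the end of the patient rows, with the chart as its source. No row holds an admission, pre-operative or change-from-baseline hemoglobin, whether as endpoint, covariate or descriptor. The text before the table states: "The detailed listing of variables below will serve as the start of a data dictionary". What it says will be added later is detailed codes for the data elements, not further elements.

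Bleeding is also recorded directly. The table has "Operative blood loss (codes as < 1000 mL vs. > 1000 mL for primary endpoint") and "Number of blood transfusions (coded as 0 vs. any for primary endpoint"). Both come from the chart, are kept in continuous as well as binary form, and belong to the primary maternal composite.

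For analysis, section 4 f) sends research question 2.2 back to the approach for question 1.1, which is a logistic regression on hospital, time and their interaction. It adds that "dependent variables for these analyses will include the individual component items of the primary endpoints", along with the listed secondary endpoints. The sample is "480 infant/maternal patients (120 Regions before/120 after simulation; 120 Methodist before/120 after simulation"). The covariate rule reads: "Covariates in regression analysis will be specified a-priori on the basis of theory and when such covariates are unbalanced in comparison groups". It names neither hemoglobin nor transfusion. On status, the plan states: "Inferential analysis of secondary endpoints will be considered exploratory with the known limitation that multiple testing could yield type 1 errors".

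**The concern.** A hemoglobin value at discharge is the sum of three things: where the woman started, how much blood she lost, and how much she was given. The plan collects only the sum. Three consequences follow.

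- **Precision.** Variation in starting hemoglobin has nothing to do with the training, but it inflates the standard error of the contrast. The covariate rule cannot remove it, because the value is not collected.
- **Bias.** If antenatal anemia changes over time at one hospital and not at the other, the change passes into the hospital-by-time contrast and cannot be told apart from a training effect.
- **Attenuation.** If training reduces heavy bleeding, it also reduces transfusion. The transfusions avoided would have raised discharge hemoglobin, so part of the gain is cancelled, mainly among the women who bleed most.

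At stake is the reading of one exploratory result. A null finding on hemoglobin could be taken as evidence that bleeding did not fall, when the measure was noisier and less responsive than it needed to be.

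**Working it through.** **The plan's own figure.** Section 4 g) gives no SD, effect size or power for hemoglobin. Its only patient-level figure is 80% power for the maternal composite. That figure reproduces as a two-group comparison of 120 with 120 at two-sided 0.05. With h = 2·asin√p1 − 2·asin√p2 and power = Φ(h·√60 − 1.96), 20% vs 8% gives 78.2%, 30% vs 15% gives 80.5%, and 40% vs 23% gives 81.6%. It says nothing about hemoglobin, so the rest rests on stated assumptions.

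**Precision.** Inputs from the plan: four independent cells of 120, two-sided alpha 0.05, power 80%. Assumed: r, the within-cell correlation of admission with discharge hemoglobin, and a common SD.

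- Unadjusted: MDE = (1.960 + 0.842) × SD × √(4/120) = 2.802 × 0.1826 SD = 0.51 SD.
- Adjusted for admission value: multiply by √(1 − r²).
- Simple change score: multiply by √(2(1 − r)).

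| r (assumed) | Unadjusted | Covariate-adjusted | Change score |
|---|---|---|---|
| 0.3 | 0.51 | 0.49 | 0.61 |
| 0.5 | 0.51 | 0.44 | 0.51 |
| 0.7 | 0.51 | 0.37 | 0.40 |

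The adjusted standard error is lower by 5%, 13% and 29% respectively. At r = 0.5, 120 × (1 − 0.25) = 90 women per cell with adjustment give the precision of 120 without it. A change score is worse than the raw value below r = 0.5, equal at 0.5, and never better than adjustment at these values.

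**Bias.** Let δ be the change in mean admission hemoglobin at Regions minus that at Methodist, and β the slope of discharge on admission hemoglobin. The unadjusted contrast then carries a bias of β × δ. A constant difference between hospitals, or a trend shared by both, gives δ = 0 and no bias.

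**Attenuation.** This was simulated on assumed values only:

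- admission hemoglobin with mean 12 and SD 1.1 g/dL
- log-normal blood loss with median 900 mL and log-SD 0.45
- a fall of 2 g/dL per litre lost, with residual SD 0.5
- blood loss cut by 20% through training
- transfusion when the post-operative value falls below a cut-off of 7, 7.5 or 8 g/dL, raising hemoglobin by 1 or 2 g/dL. The cut-offs are a modelling device to vary the transfusion rate and make no clinical statement.

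| Transfused before → after the cut | Rise (g/dL) | Mean benefit before transfusion → at discharge (g/dL) | Loss overall | Loss in heaviest-bleeding tenth |
|---|---|---|---|---|
| 3.2% → 1.3% | 1 | 0.40 → 0.38 | 5% | 17% |
| 3.2% → 1.3% | 2 | 0.40 → 0.36 | 10% | 34% |
| 5.6% → 2.6% | 1 | 0.40 → 0.37 | 8% | 23% |
| 5.6% → 2.6% | 2 | 0.40 → 0.34 | 15% | 45% |
| 9.4% → 4.9% | 1 | 0.40 → 0.35 | 11% | 26% |
| 9.5% → 5.0% | 2 | 0.40 → 0.31 | 23% | 53% |

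The effect shrinks in every scenario. It neither vanishes nor reverses in any of them.

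**The case against.** The strongest reply is that the plan never presents discharge hemoglobin as its measure of bleeding. A reader might infer that it does, and that benefit in the heaviest bleeders would be hidden. The documents do not support this: blood loss and transfusion are recorded directly, form part of the primary composite, and are analysed individually under question 2.2. Fewer heavy bleeds or transfusions would show there. Discharge hemoglobin can also fairly be read as the mother's anemia status on leaving hospital. On that reading the value after any transfusion is the quantity wanted, and attenuation is not a defect. This stands, and it is why discharge hemoglobin should remain the endpoint, with transfusion handled in a sensitivity analysis only.

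A second reply is that the design protects against baseline differences. It does so for stable hospital differences and shared trends. It does not protect against a differential shift, though nothing in the documents suggests that one occurred. The loss of precision remains in either case.

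Third, the gain may be modest. If the true effect were 0.15 g/dL and the SD 1.0 to 1.5 g/dL (both assumed), adjustment at r = 0.7 would give a power of only 12 to 21%. That is fair: adjustment sharpens the estimate but does not make small effects detectable.

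Finally, replacing the endpoint with the lowest value before transfusion would bring its own problems. Such a value may not exist for women transfused during surgery, so it would be missing selectively among heavy bleeders, and a lowest value depends on how often blood is drawn. This also stands.

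**Conclusion.** The concern holds in limited form. The hemoglobin endpoint is analysed raw, with no baseline collected and no rule for transfused women, and its two rows conflict on source. Adjustment for admission hemoglobin would lower the minimum detectable differential change from 0.51 SD to 0.49, 0.44 or 0.37 SD at r = 0.3, 0.5 or 0.7. The documents give no value for r, for the SD or for the transfusion rate, so the true size is unknown.

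A reader might go further and infer that most of a real benefit is lost. For example, suppose training prevents heavy bleeding in 5% of women, each with an extra fall of 3 g/dL, and transfusion restores 2 g/dL. The benefit of 0.05 × 3 = 0.15 g/dL then appears as 0.05 × (3 − 2) = 0.05 g/dL, a loss of two thirds. That requires every prevented bleed to have been transfused. If half would have been, 0.05 × (3 − 1) = 0.10 g/dL appears and one third is lost. The simulated range was 5 to 23% overall. Attenuation is the right word, and no figure for it can be drawn from the documents.

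No primary conclusion depends on this. It is an inexpensive improvement to one exploratory analysis.

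**What to change.** - Add admission (pre-operative) hemoglobin to the Clarity pull and to the variable table as a covariate.
- Specify a linear model for discharge hemoglobin with hospital, time, their interaction and admission hemoglobin. The logistic model carried over from question 1.1 does not fit a continuous outcome. Include the covariate whether or not the groups look unbalanced, and do not use a simple change score.
- Keep one hemoglobin row with one data source.
- As a sensitivity analysis only, handle transfused women explicitly: use the last pre-transfusion value where one exists, or a ranked outcome that places transfused women worst. Do not enter transfusion as an ordinary covariate. It occurs after exposure and is itself an outcome, so adjusting for it would remove part of the effect.
- State how women without an admission value will be handled.

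The cost is one more laboratory field in a programmatic pull; section 4 c) already foresees pulls at several times. If extraction is complete, as the timeline and the document date make possible, a supplementary pull is needed. It must take place while records can still be linked, since section 7 provides for early destruction of identifiers. The remaining downside is that some women may have no admission value.

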Members of the study team have verified the accuracy of this method of identifying cesarean section during the second stage of labor by cross-checking a Clarity pull of EMR data with chart audit for a random sample of 10 patients.

Medical staff inclusion criteria: all 120 staff members (staff physicians, residents, nurses, surgical technicians) at Regions hospital who practice in the Birth center who underwent required simulation education regarding delivery of deeply impacted fetal heads during second stage cesarean section (50 physicians and 65 nurses and 5 techs) and completed the surveys as part of the QI simulation project.

ii. Sample size

Patients: A data pull conducted by an HP Institute RIIS programmer in September 2017 indicated that there are 80 patients per year at Regions hospital having second stage cesarean sections and 80 patients per year at Methodist hospital having second stage cesarean sections. This study will gather data via programming and chart audit on the following counts of patients in these time period:

- A. July 1, 2014 – June 30, 2015 (80 Regions patients)
- B. July 1, 2015 – June 30, 2016 (80 Regions patients)
- C. July 1, 2016 – December 31, 2017 (120 Regions, 120 Methodist) - 18 mo PRE period
- D. January 1, 2018 – June 30, 2019 (120 Regions, 120 Methodist) - 18 mo POST period

Different subsets of patients will be used for different research questions. For research questions 1.1, 1.2, 2.2 Group C above will serve as the pre-period patients and Group D for post-period patients. Thus, the total patient sample size for these research question is expected to be n=480. For research question 2.3, in addition to Groups C and D, we will also include utilize the 160 patients from Regions in Groups A and B for a sample size of 400 at Regions and 240 at Methodist (n=640 total).

Medical staff sample size: The simulation center staff will survey 120 staff (50 physicians, 65 nurses, and 5 techs) immediately before and after the required simulation education as part of an existing QI project. This QI project data will be used to address

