providers from other groups performing cesarean sections. Residents are consistent over a period of 4 years. The Regions Hospital birth center has protocols for cesarean sections that are standard for all patients undergoing this procedure. The study outcomes should be easily compared without variations in cesarean section protocol. At Regions Hospital, team simulation events are organized with the simulation center staff throughout the year for other obstetrical emergencies such as shoulder dystocia, postpartum hemorrhage and hypertensive emergencies. We have the support of the birth center administration for this study

6. Risks and Benefits

There should not be risks to mothers, babies, and providers with this study. There is minimal risk to conducting this study; it is a retrospective, data-only study.

Benefits may include:

Knowledge of whether simulation training improved maternal and perinatal outcomes in patients with deeply impacted fetal head at cesarean section, staff and provider teamwork, and staff and provider morale.

7. Data Confidentiality and Privacy

Data will be stored on secure servers with limited access. Servers are in a physically secure location on campus and backed up nightly. Data will also be protected by username and password requirements.

Data will be kept separately from patient identifiers. Identifiers will be destroyed at the earliest opportunity and data shared with the statistician will be completely de-identified.

Patient identifiers will not be printed at any time during the study.

8. Timeline

Mid October-mid December 2017: QI project. Hold 6 simulation events for the impacted heat at cesarean section scenario. Each scenario will be 2 hours in length and mandatory for all Regions Hospital birth center providers, residents, nursing staff and techs. Will administer pre and posttest questionnaire before and after simulation event.

December 2017- June 30th 2019: Study data extraction via Epic and chart review, from charts of patients undergoing second stage cesarean sections from pre and post simulation time periods.

June 2018: QI project. Administer staff questionnaire 6 months after simulation event.

June 2019: Data and statistical analysis and presentations and manuscript write up.

9. Dissemination/Sharing Results/Integration and Impact

Submit manuscript to peer reviewed journal

Research poster at the GME event in May 2018 and 2019

Resident research presentation May 2019

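### The outcome models (RQ 1.1, 1.2, 2.2) make no allowance for patients sharing an operator: a small risk to the interaction test, and too-narrow 95% intervals for each hospital and period

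*Combined protocol and SAP*

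**What the plan says.** Section 4 f, RQ 1.1, gives the model: "Logistic regression will be used to predict the composite maternal morbidity endpoint (0/1) from hospital (Regions, Methodist), time (pre or post simulation), and their interaction". Support for the hypothesis requires "A significant hospital * time interaction and pattern of effects showing more improvement over time in Regions than Methodist". The same paragraph promises proportions, standard errors and 95% intervals for each hospital at each time point, for change over time, and for differential change. RQ 1.2 and RQ 2.2 reuse the approach. Under all three questions the SAP adds that "Each sample of 120 is viewed as an independent sample". No random effect, GEE or cluster-robust standard error is named.

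The cells are set in section 4 b ii: "120 Regions, 120 Methodist) - 18 mo PRE period" and "120 Regions, 120 Methodist) - 18 mo POST period".

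On operators:
- Section 4 b i counts the trained staff as "50 physicians and 65 nurses and 5 techs".
- Section 5 says that no outside group performs cesareans at Regions, calls the workforce relatively stable, and adds that "Residents are consistent over a period of 4 years".
- Section 3 (QI Project Description) plans three extra sessions for new staff.
- The variable table in section 4 d has one operator item, "Person doing the head extraction (staff or resident"), binary and drawn from the EMR. It has no operator identifier.

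**The concern.** The training acts on operators, and outcomes such as uterine extension, blood loss and operative time plausibly depend on who operates. Two patients delivered by the same operator are then more alike than two patients of different operators, and ordinary logistic standard errors ignore this.

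Two outputs are exposed. One is the hospital-by-time interaction, on which the conclusion mainly rests. The other is the set of intervals for each hospital in each period. Operator effects shared by both periods cancel from the first but not from the second. Operator clustering is not among the limitations in section 4 h.

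**Working it through.** **Inputs from the documents.** 120 patients per hospital and period; 50 Regions physicians trained; two-sided alpha 0.05. Average caseload is 240/50 = 4.8 deliveries per physician over 36 months, or m = 120/50 = 2.4 per period.

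**Assumed, because the documents are silent.** ICC 0.02 to 0.10; even caseload or a coefficient of variation (CV) of 1; 50 or 20 operators; the same structure at Methodist; and r, the share of the operator effect common to both periods. Half turnover means r = 0.5 and one-quarter turnover r = 0.75.

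**Step 1: the plan's own figure.** Section 4 g states 80% power for 20% vs 8%, 30% vs 15% and 40% vs 23%. For 120 vs 120, power = Φ(h√(120/2) − 1.96), where h is the difference in 2·arcsin√p. This gives 78.2%, 80.5% and 81.6%. The stated figure is therefore reproduced as a comparison of two independent groups with no design effect.

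**Step 2: the interaction.** The variance relative to the model's is

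V = 1 + (m − 1)·ICC − m·ICC·r,

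with m replaced by m(1 + CV²) for uneven caseloads, so 2.4 becomes 4.8 at CV = 1. The ratio of true to model standard error is √V, and type I error is 2[1 − Φ(1.96/√V)].

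Example: 50 operators, uneven, ICC 0.10, r = 0.5 gives V = 1 + 0.38 − 0.24 = 1.14, so √V = 1.068 and type I error is 6.6%.

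Results at ICC 0.10, the top of the range:

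| Operators per hospital | r = 1 | r = 0.75 | r = 0.5 | r = 0 |
|---|---|---|---|---|
| 50, even (m = 2.4) | 0.949 (3.9%) | 0.980 (4.6%) | 1.010 (5.2%) | 1.068 (6.6%) |
| 50, uneven (4.8) | 0.949 (3.9%) | 1.010 (5.2%) | 1.068 (6.6%) | 1.175 (9.5%) |
| 20, even (6) | 0.949 (3.9%) | 1.025 (5.6%) | 1.095 (7.4%) | 1.225 (11.0%) |

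With 20 operators, uneven caseload (m = 12) and r = 0.5, V = 1 + 1.1 − 0.6 = 1.5, which gives 1.225 and 11.0%.

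The ratios below 1 come from holding caseloads fixed. Simulation lets deliveries fall at random on operators (30% event rate, 120 per cell, ICC on the latent scale):

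- Same operators in both periods, 20 or 50: ratio 0.995 to 1.012, type I error about 5%.
- 50 operators, CV 1, one quarter replaced: 1.01 to 1.04, 5.1% to 5.9%.
- 50 operators, CV 1, 3/8 replaced: 1.03 to 1.06, 5.6% to 6.5%.
- 50 operators, CV 1, half replaced: 1.03 to 1.07, 5.6% to 6.7%.
- 20 operators, CV 1, half replaced: 1.04 to 1.19, 6.0% to 9.9%.

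The 3/8 figure is 18 months between window midpoints divided by a 48-month residency. It applies to residents only, so the whole pool should turn over less if staff physicians are stable.

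**Step 3: intervals for each hospital and period.** Nothing is differenced here, so r drops out: D = 1 + (m − 1)·ICC and coverage = 2Φ(1.96/√D) − 1. The target is the rate averaged over operators.

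- 50 operators, even: D = 1.028 to 1.14, coverage 94.7% to 93.4%.
- 50 operators, uneven: D = 1.076 to 1.38, coverage 94.1% to 90.5%.

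Simulation gives about 90% to 94% with 50 operators and 84% to 93% with 20, even with no turnover.

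**The case against.** The strongest reply is that the effect on the primary test is small and its direction is not fixed. Operators who work in both periods largely cancel from a pre-post contrast. With even, fixed caseloads of 2.4, the model's standard error is too small only when m(1 − r) > 1, that is, when more than about 42% of the operator effect is not shared (1/2.4 = 0.417). Section 5 describes a stable workforce. This stands. It limits the point on the interaction but does not reach the per-period intervals.

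A reader might infer that the interaction standard error and p-value are simply wrong. The documents do not support that, because the size depends on quantities they do not give and is close to nil with the same operators throughout. Nor do they support type I error near 10% or above. The highest simulated value, 14.5%, needs every operator replaced, which conflicts with section 5, and no document suggests as few as 20 operators.

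A reader might also take 50 as a ceiling on operators. It is the number trained in late 2017. With half replaced and 50 working in each period, 50 + 25 = 75 would have operated.

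The quoted independence sentence, read literally, concerns separation of the four samples. Independence within a sample follows from the ordinary logistic model, not from that sentence. Finally, the SAP does not rest on significance alone: it also requires a pattern favoring Regions and attributes it to training only as a possibility.

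**Conclusion.** The point holds as a minor to moderate weakness. The models for RQ 1.1, 1.2 and 2.2 ignore clustering within a limited pool of operators, and the planned variables would not allow it to be checked.

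Assuming 50 operators per hospital and latent ICC 0.02 to 0.10, the interaction standard error is about right with the same operators in both periods. With one quarter to one half turnover, the true value is up to about 7% larger than the model's, with type I error about 5% to 6.5%. About 11% needs 20 operators, uneven caseload and half turnover together. If operators respond differently to training, r falls below 1 even without turnover.

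The clearer defect is in the intervals for each hospital and period. They are too narrow at every turnover level, with coverage about 90% to 94% on the same assumptions; at the lowest ICC with even caseload the shortfall is negligible.

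**What to change.** Add a coded operator identifier to the Clarity pull, with one code per operator across both periods. State which role defines the cluster, the person extracting the head or the responsible surgeon, since section 4 d separates staff from residents. Do this before the identifiers are destroyed, because section 7 plans that early and gives the statistician only de-identified data.

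Report the RQ 1.1, 1.2 and 2.2 models with standard errors clustered by operator and a small-sample correction, or with operator and operator-by-period random intercepts. State in section 4 f that independence of patients within a sample is no longer assumed.

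The cost is one extra EMR field, a changed standard-error option and slightly wider intervals. None of this cures having one hospital per arm: hospital-by-period variation cannot be estimated by any operator-level adjustment. Section 4 h notes that the two systems may not be comparable, and it should list this limitation as well.
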